#### Data Analysis & Statistical Considerations

The approach to analysis will be primarily descriptive. Demographics, questionnaire data, and testing results will be reviewed and summarized using graphical techniques and summary statistics. Where applicable, exact method confidence intervals will be computed around point estimates. Trends over time will be evaluated graphically. The proportion of participants adhering to social distancing guidelines after a positive vs. negative test result will be compared using tests of proportion clustered by participants with various levels of intra-participant correlation. Stratified analyses by test or week number will also be performed. We will explore the associations between positive test results and critical behavioral measures using mixed modeling techniques to account for the participant and household correlations. Analyses will be conducted using SAS (SAS Institute, Cary NC) and R with R Studio (R-project). Point estimates with 95% confidence intervals will be reported. The analysis will be done for applicable study populations as described above, and stratified by participant demographics of

interest (e.g., age, gender). There will be a comparison of the proportion of participants that report adhering to social distancing guidelines after positive vs. negative test result.

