A participant could scan a QR code on the participant instruction card or the You & Me COVID-Free bag to access a 1-minute Front Door Survey each time she/he takes a swab test. Individuals will also be invited to complete a more detailed Baseline Survey, which will take about 20 minutes, and then another short follow-up survey (i.e., End of Study Survey) about four weeks later. There is no consent required for each completion of the Front Door Survey and scanning the QR code will start the Front Door Survey automatically. Immediately following the Front Door Survey, the participant is asked if they would like to participate in the sub study. If they agree, they are asked to sign an informed consent form and then given the Baseline Survey to complete. The End of Study Survey is administered 28 days following the completion of the Baseline Survey. The participants who fill out the Baseline Survey and the End of Study Survey will be included in the sub study if they provide a signed and dated informed consent form. There are no exclusion criteria.

As the at-home tests are authorized for children ages 2 and up, these children may also participate in at-home testing, but they will not be enrolled as participants themselves. For children 2 to 14 years of age, an adult must collect the sample and complete the test procedure. Data will be obtained from participants at the individual level.

The Front Door Survey is administered after each swab test by scanning the QR code. There is no consent needed for the Front Door Survey. Immediately following the Front Door Survey, the Baseline Survey is administered at the time of informed consent. The End of Study Survey is administered 28 days following the completion of the Baseline Survey.

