The Front Door Survey and the Baseline/End of Study Surveys cannot be linked due to the way they were set up, despite the fact that there are matching record IDs. Each entry in the Front Door Survey corresponds to a unique test result. Multiple test results can correspond to the same participant, but each test result receives a unique record ID so there is no way to link the multiple results to one participant. Each participant can sign up once to take the Baseline Survey and End of Study Survey, and each unique record ID represents one participant in the Baseline and End of Study Surveys. An observation from the Baseline and End of Study Surveys will have the same record ID as an observation in the Front Door Survey. However, this does not necessarily mean that the information across both sets of surveys are from the same participant. In order to clarify the data flow of the YMCF project, the consort diagram in Figure 1 presents data from the Front Door Survey on the number of total entries, the number of valid test results, and completeness of the primary outcomes. It also presents data from the Baseline Survey on the and number of total participants, the number of consented participants, and completeness on secondary outcomes. The primary outcomes correspond to the Front Door Survey and are:

- Participant reasons for test use
- Test result
- Current vaccination status

- Likelihood of future vaccination
- Perspective on easiest way to obtain free oral COVID medicines

Among 2,399 valid-test-result entries in Front Door Survey, 412 entries completed full set of primary outcomes, 1,987 entries partially completed primary outcomes, and none entry were missing all primary outcomes. See details in Table 1.

Table 1. Missingness of Primary Outcomes in Front Door Survey

	Participant reasons for test use	Test result	Current vaccination status	Likelihood of future vaccination	Perspective on easiest way to obtain free oral COVID medicines
Missing	0	0	4	1987	0
Not missing	2399	2399	2395	412	2399
Total	2399	2399	2399	2399	2399

The secondary outcomes correspond to the Baseline Survey and are:

- Participant attitudes towards SARS-CoV-2 vaccination
- Accessibility to personal protective equipment and distancing in the work place
- Self-report COVID-19 testing and symptoms

[figure not shown]

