Test kits consisting of 2 tests per kit were distributed to Merced County households starting on November 18, 2021, through the Merced County Health Department and a coalition of community groups. Outreach and public awareness were done through a multi-pronged education and marketing program including mailers, door hangers, billboards, social media campaigns and targeted ads on local media outlets. Test kit distribution ended on December 31, 2021 and 200,000 test kits were distributed.

Text messages reminders were sent out to all study participants automatically using Twilio, with REDCap as the backend. The messages will include links to complete three surveys, i.e., Front Door Survey, Baseline Survey, and End of Study Survey (28 days later). Participant phone numbers will be provided to Twilio to facilitate the sending of text messages, and Twilio may store metadata about the delivery of the messages, such as successful or failure, and time and date stamps, but no other content will be stored. Messages for this study are one-way only and cannot be replied to.

Outcome Variables

- Primary Outcomes (from Front Door Survey)
 - Participant reasons for test use
 - Participant test result
 - Participant current vaccination status
 - Participant likelihood of future vaccination
 - Participant perspective on easiest way to obtain free oral COVID medicines
- Secondary Outcomes (from Baseline Survey)
 - Participant attitudes towards SARS CoV-2 vaccination
 - Proportion of reasons for getting/not getting a COVID-19 vaccination
 - Participant accessibility to personal protective equipment and distancing in work place
 - Proportion of respondents on access to necessary personal protective and distancing
 - Participant self-report COVID-19 testing and symptoms
 - Proportion of respondents on COVID-19 testing method, testing history and result, accessibility to testing
 - Proportion of respondents who report current symptoms

Handling of Missing Data

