- v) perceived COVID-19 medication access

Analysis: Sociodemographic factors and outcomes will be drawn from the Front Door Survey. For the outcome i) reasons for test use, we will run a logistic regression model on each of the possible choices since participants could choose all that applied. For the outcomes ii) and iii), logistic regression will be used. For the outcome iv) likelihood of future vaccination, ordinal logistic regression will be used. For the outcome v), we will run a logistic regression model on each of the possible answers. Odds ratio estimates and 95% confidence interval will be presented in Table 6.

The methods described above will constitute the main analysis of these primary outcomes. The hypothesis is defined as:

$$H_0: \beta_i = 0$$

$$H_a: \beta_i \neq 0$$

And the logit is the linear function: $\ln(\frac{P}{1-P}) = \alpha + \beta_1 x_1 + \beta_2 x_2 + \dots + \beta_k x_k$

Where β_i is the parameter coefficient of independent variable x_i , and p represents the true probability that the dependent variable $y=1$ (event) given the numeric values on the independent variables. This analysis will be conducted using PROC LOGISTIC in SAS. The hypothesis as expressed above will be tested at a 2-sided significance level of 0.05.

Crucial assumption that must be met for logistic regression is linearity in the logit for continuous independent variables. We will use the Box-Tidwell test and scatter plot to check for linearity between the continuous predictors and the logit. If the linearity assumption is violated, it is necessary to make further adjustments either to the model (including or excluding predictors), or transforming the response and/or predictors. We will use restricted cubic splines to explore non-linear continuous associations.

It is important to note that the independence assumption for the logistic regression models may be violated since a single participant can enter multiple records in the Front Door Survey, but cannot be distinguished. If the violation is occurring then our models are underestimating standard errors, leading to inflated Type I error.

- See Appendix for proposed:
 - o Table 6: Regression estimates for the association between sociodemographic factors and COVID-19 testing, vaccination, and medication outcomes

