Complete survey for self	xxx (xx.x%)
Complete survey for child	xxx (xx.x%)
(missing)	xxx (xx.x%)
Race^c	
White	xxx (xx.x%)
Black or African American	xxx (xx.x%)
American Indian or Alaska Native	xxx (xx.x%)
Asian (including South Asian and Asian Indian)	xxx (xx.x%)
Native Hawaiian or Pacific Islander	xxx (xx.x%)
Some other race	xxx (xx.x%)
(missing)	xxx (xx.x%)
Ethnicity	
Hispanic	xxx (xx.x%)
(missing)	xxx (xx.x%)
Main Reason for testing	
I wanted to be sure I/my child did not have COVID-19 before being around others	xxx (xx.x%)
I/my child had COVID-19 like symptoms	xxx (xx.x%)
I/my child was in close contact with someone who might have COVID-19	xxx (xx.x%)
I/my child was in close contact with someone who tested positive for COVID-19	xxx (xx.x%)
Someone in my household might have COVID-19	xxx (xx.x%)
Someone in my household tested positive for COVID-19	xxx (xx.x%)
Other	xxx (xx.x%)
(missing)	xxx (xx.x%)
COVID-19 test result	
Positive	xxx (xx.x%)
Negative	xxx (xx.x%)
(missing)	xxx (xx.x%)

Receive at least one dose of a COVID-19 vaccine	xxx (xx.x%)
(missing)	xxx (xx.x%)
Likelihood of future COVID-19 vaccine	
Very likely	xxx (xx.x%)
Somewhat likely	xxx (xx.x%)
Not very likely	xxx (xx.x%)
Not at all likely	xxx (xx.x%)
(missing)	xxx (xx.x%)
Easiest way to get free COVID-19 oral medications	
An urgent care center	xxx (xx.x%)
A doctor's or other health professional's office	xxx (xx.x%)
A mobile health unit	xxx (xx.x%)
A drug store/pharmacy	xxx (xx.x%)
A grocery store	xxx (xx.x%)
A community center	xxx (xx.x%)
A place of worship	xxx (xx.x%)
A community park	xxx (xx.x%)
A neighborhood school	xxx (xx.x%)
Other	xxx (xx.x%)
(missing)	xxx (xx.x%)

Note:

- a. The total entries reflect number of entries in Front Door Survey that have a valid SARS CoV-2 test response (i.e., positive or negative).
- b. Age Category is based on participant's response on the question *I am completing this survey for* each entry. If participants chose *Myself* or *Another household member* in their entries, they presumably were Adult; likewise, if *A child* were chosen in their entries, the participants presumably were children. However, there is no guarantee that *Myself* or *Another household member* is an adult, or *A child* is a child. No other valid information can be linked with Front Door Survey to identify the actual age category.
- c. Participants could check all Race that apply.

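### Objective 5 tests up to 2,399 unlinked per-test entries as independent; the SAP concedes that repeat entries would understate standard errors, yet plans no sensitivity range, and Table 6 bolds p<.05 without a caveat

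*SAP*

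**What the plan says.** The unit of record is a test. Under Study Population, the SAP says: "The Front Door Survey is administered after each swab test by scanning the QR code." It adds: "Multiple test results can correspond to the same participant, but each test result receives a unique record ID", and that these results cannot be traced back to one person. Under Intervention: "Test kits consisting of 2 tests per kit were distributed to Merced County households". The Table 5 shell in Appendix I has a row for "Complete survey for child", and its note b allows entries for another household member.

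Objective 5 draws covariates (age category, race, ethnicity, preferred language) and outcomes from these entries. It uses binary and ordinal logistic regression in PROC LOGISTIC at two-sided 0.05, with no clustered or robust variance. It gives the results primary status: "The methods described above will constitute the main analysis of these primary outcomes."

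Objective 5 then notes that one participant may enter several indistinguishable records: "If the violation is occurring then our models are underestimating standard errors, leading to inflated Type I error." No remedy follows. For non-linearity, the same text sets out a check and corrective steps.

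The Table 6 notes bold estimates with p<.05 and do not mention dependence. Note e describes the N as participants, whereas Table 5 note a describes it as entries.

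For its own comparison of social distancing after positive and negative results, the protocol (Data Analysis & Statistical Considerations) planned "tests of proportion clustered by participants with various levels of intra-participant correlation". For associations between test results and behaviour it planned models "using mixed modeling techniques to account for the participant and household correlations".

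**The concern.** Age category, race, ethnicity and language are essentially fixed within a person, and the last three are often shared in a household. When such a covariate is tested on positively correlated entries as if they were independent, the standard error is too small. The SAP acknowledges this for repeat entries by one participant. It does not mention household members, although kits go to households and entries may be made for a child or another member.

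What is at stake is how Table 6 is read. If repeats are common, the intervals for race, ethnicity and language are too narrow by an unstated amount, and some bolded odds ratios may not hold. The effect should be greatest for stable person-level outcomes (vaccination status, likelihood of future vaccination). It should be smaller for reasons for testing and test result, which can change between tests.

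A reader could not repair this well from the published table, because the shell prints one decimal.

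**Working it through.** **The plan's own count.** 2,510 entries less 111 without a valid result (Handling of Missing Data) = 2,399. The missingness table under Study Population agrees: 412 + 1,987 = 2,399 for likelihood of future vaccination and 2,395 + 4 = 2,399 for vaccination status. So 2,399 is a ceiling. The likelihood model has at most 412 entries, and Table 6 also requires complete sociodemographic data.

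**Inputs not given.** Entries per person and the within-person or within-household correlation are absent. The values below are assumptions. Two entries per person is anchored only on two tests per kit.

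**Formulas.** For a person-level covariate, m entries per person and correlation r:

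- DEFF = 1 + r × (Σm²/Σm − 1). If a share p of people make two entries and the rest one, DEFF = 1 + r × 2p/(1 + p).
- True Type I error = 2 × (1 − Φ(1.96/√DEFF)). At DEFF = 1 this returns 0.05.

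| Assumed pattern | r | DEFF | Type I error |
|---|---|---|---|
| 10% of people make two entries | 0.25 | 1 + 0.25 × 0.20/1.10 = 1.045 | 0.055 |
| 25% make two | 0.25 | 1 + 0.25 × 0.50/1.25 = 1.10 | 0.062 |
| 50% make two | 0.5 | 1 + 0.5 × 1.0/1.5 = 1.333 | 0.090 |
| All make two | 1 | 2.0 | 0.166 |
| All make three | 0.5 | 2.0 | 0.166 |
| All make three | 1 | 3.0 | 0.258 |
| 10% make five, the rest one | 1 | 3.4/1.4 = 2.43 | about 0.21 |

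The last row averages only 1.4 entries per person, so the two-entry case is not a bound.

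**Simulation check.** With 2,399 entries, a binary person-level covariate (50%), outcome prevalence 30%, a naive Wald test and 20,000 runs, the first four rows gave 0.056, 0.060, 0.086 and 0.166. Three entries at r = 1 gave 0.260. With 412 entries, the first and fourth rows gave 0.055 and 0.165.

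**Effect on a reported p-value.** The naive p needed for a true 0.05 is 2 × (1 − Φ(1.96 × √DEFF)). The tipping design effect, at which significance is lost, is (z/1.96)².

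| DEFF | Log-scale CI width factor | Naive p needed |
|---|---|---|
| 1.25 | 1.118 | 0.028 |
| 1.5 | 1.225 | 0.016 |
| 2 | 1.414 | 0.0056 |
| 3 | 1.732 | 0.0007 |

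Naive p of 0.04, 0.02, 0.01 and 0.005 tip at DEFF 1.10, 1.41, 1.73 and 2.05.

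**Worked example.** Take an odds ratio of 1.30 with naive p = 0.01: ln 1.30 = 0.2624, SE = 0.2624/2.576 = 0.1019. Multiplying the SE by √DEFF gives:

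- naive: 1.06 to 1.59
- DEFF 1.5: 1.02 to 1.66
- DEFF 2: 0.98 to 1.72
- DEFF 3: 0.92 to 1.84

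In the one-decimal shell this prints as 1.3 (1.1 to 1.6). Working back, z = ln 1.3/((ln 1.6 − ln 1.1)/3.92) = 2.745, which implies a tipping design effect of (2.745/1.96)² = 1.96. The true value is 1.73.

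**A limit.** If the covariate differs within each pair, as age category can within a household, positive correlation works the other way. In simulated pairs with r = 0.5, naive Type I error was 0.006.

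**The case against.** The strongest reply is that the SAP already discloses the problem, its cause and its direction, immediately before the pointer to Table 6. Without identifiers nobody can estimate the size, and rescaling by assumed factors adds no data. The upper figures need three or five entries per person, for which the documents give no basis. Only 2,510 entries came from 400,000 distributed tests (2,510/400,000 = 0.6%), so universal repeat reporting is only an assumption. The aim is exploratory and the protocol's approach is primarily descriptive. The protocol's range of correlations was meant for a different comparison. One design effect does not suit every covariate, and seven outcomes by seven coefficients with four extra intervals each is 196 more intervals.

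Much of this stands. The magnitude is unknown and may be negligible, the protocol and SAP do not contradict each other here, and the mixed models cannot be fitted to these entries. Even so, the disclosure covers only repeats by one participant and is missing from the table where the bolding appears. The SAP also states hypotheses, sets alpha at 0.05 and calls this the main analysis of the primary outcomes. An unknown size is a reason to show a range, and the protocol shows that assuming a range of correlations is a device the team already had in view. The table-size point is met by a companion table, and the age point by a stated limit.

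**Conclusion.** The concern holds. The plan tests unlinked per-test entries as independent, concedes the likely direction of error, and neither explores its size nor carries the caveat into Table 6. On the illustrative assumptions, true Type I error runs from 5.5%, which is negligible, to 16.6% with at most two entries per person, and to 25.8% with three perfectly correlated entries each. These figures assume a covariate constant within the person and positive within-person correlation; household correlation could add to them for shared covariates. None is an estimate for this study. Confidence is high that the gap exists, but the documents cannot show how much it matters. Because a naive p of 0.04 falls at a design effect of 1.10, even modest repetition could change which estimates deserve bolding. It should be fixed before Table 6 is reported.

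**What to change.** 1. In Table 6 or a companion table, beside the naive 95% intervals, give intervals with the SE multiplied by √DEFF at 1.25, 1.5 and 2, plus a higher value such as 3 for household correlation or more than two entries per person. State that the range is assumed, not estimated, and that its upper values matter mainly for vaccination status and likelihood of vaccination.
2. For each estimate with p<.05, print the tipping design effect (z/1.96)² from unrounded estimates and say up to what design effect the result holds. Do not call any result robust outright.
3. Add a Table 6 footnote that entries may not be independent within person or household, so the naive intervals and the bolding may overstate precision.
4. In note e, describe the N as entries, not participants.
5. State that the scaling suits covariates constant within a person or shared in a household (race, ethnicity, language). For age category, the range should be read as covering repeat entries only.

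The cost is SAP wording, one footnote and a spreadsheet-level rescaling of standard errors from models already planned. No new data or model runs are needed. The downside is wider sensitivity intervals and a larger table, or a second one.

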APPENDIX I - Proposed Table and Figure Listing

Table 1. Participant Sociodemographic Characteristics and Medical History in Baseline Survey in Merced County, CA

Characteristic	Minor (N=xxx)	Adult (N=xxx)	All Respondents (N=xxx) ^a
Age			
Median age in years	xx.x	xx.x	xx.x
(Missing)	xxx (xx.x%)	xxx (xx.x%)	xxx (xx.x%)
Race^b			
White	xxx (xx.x%)	xxx (xx.x%)	xxx (xx.x%)
Black or African American	xxx (xx.x%)	xxx (xx.x%)	xxx (xx.x%)
American Indian or Alaska Native	xxx (xx.x%)	xxx (xx.x%)	xxx (xx.x%)
Asian (including South Asian and Asian Indian)	xxx (xx.x%)	xxx (xx.x%)	xxx (xx.x%)
Native Hawaiian or Pacific Islander	xxx (xx.x%)	xxx (xx.x%)	xxx (xx.x%)
Some other race	xxx (xx.x%)	xxx (xx.x%)	xxx (xx.x%)
(Missing)	xxx (xx.x%)	xxx (xx.x%)	xxx (xx.x%)
Ethnicity			
Hispanic	xxx (xx.x%)	xxx (xx.x%)	xxx (xx.x%)
(Missing)	xxx (xx.x%)	xxx (xx.x%)	xxx (xx.x%)
Gender Identify			
Woman	xxx (xx.x%)	xxx (xx.x%)	xxx (xx.x%)
Man	xxx (xx.x%)	xxx (xx.x%)	xxx (xx.x%)
Non-binary	xxx (xx.x%)	xxx (xx.x%)	xxx (xx.x%)
Transgender man	xxx (xx.x%)	xxx (xx.x%)	xxx (xx.x%)
Transgender woman	xxx (xx.x%)	xxx (xx.x%)	xxx (xx.x%)
Gender nonconforming	xxx (xx.x%)	xxx (xx.x%)	xxx (xx.x%)
Agender	xxx (xx.x%)	xxx (xx.x%)	xxx (xx.x%)
Bigender	xxx (xx.x%)	xxx (xx.x%)	xxx (xx.x%)
(Missing)	xxx (xx.x%)	xxx (xx.x%)	xxx (xx.x%)
Current Pregnancy^c	N/A	xxx (xx.x%)	xxx (xx.x%)
(Missing)	N/A	xxx (xx.x%)	xxx (xx.x%)
Education			

Have never gone to school	xxx (xx.x%)	xxx (xx.x%)	xxx (xx.x%)
Completed 5 th grade or less	xxx (xx.x%)	xxx (xx.x%)	xxx (xx.x%)
Completed 6 th to 8 th grade	xxx (xx.x%)	xxx (xx.x%)	xxx (xx.x%)
Completed 9 th to 12 th grade	xxx (xx.x%)	xxx (xx.x%)	xxx (xx.x%)
Completed High school graduate or GED	xxx (xx.x%)	xxx (xx.x%)	xxx (xx.x%)
Completed Some college level/Technical/Vocational	xxx (xx.x%)	xxx (xx.x%)	xxx (xx.x%)
Completed Bachelor's degree	xxx (xx.x%)	xxx (xx.x%)	xxx (xx.x%)
Completed Master's/Doctoral degree	xxx (xx.x%)	xxx (xx.x%)	xxx (xx.x%)
(Missing)	xxx (xx.x%)	xxx (xx.x%)	xxx (xx.x%)
Household Member			
Just me	xxx (xx.x%)	xxx (xx.x%)	xxx (xx.x%)
Living with spouse, no kids	xxx (xx.x%)	xxx (xx.x%)	xxx (xx.x%)
Family including kids	xxx (xx.x%)	xxx (xx.x%)	xxx (xx.x%)
Family with 3 generations	xxx (xx.x%)	xxx (xx.x%)	xxx (xx.x%)
Family with 4 generations	xxx (xx.x%)	xxx (xx.x%)	xxx (xx.x%)
Living with roommates	xxx (xx.x%)	xxx (xx.x%)	xxx (xx.x%)
(Missing)	xxx (xx.x%)	xxx (xx.x%)	xxx (xx.x%)
Transitional Housing/Shelter/Homelessness			
(Missing)	xxx (xx.x%)	xxx (xx.x%)	xxx (xx.x%)
Congregate Housing			
Group care setting	xxx (xx.x%)	xxx (xx.x%)	xxx (xx.x%)
Nursing home	xxx (xx.x%)	xxx (xx.x%)	xxx (xx.x%)
Residential care facility for disabled people	xxx (xx.x%)	xxx (xx.x%)	xxx (xx.x%)
Psychiatric treatment facility	xxx (xx.x%)	xxx (xx.x%)	xxx (xx.x%)
Group home	xxx (xx.x%)	xxx (xx.x%)	xxx (xx.x%)
Board and care home	xxx (xx.x%)	xxx (xx.x%)	xxx (xx.x%)
Prison or jail	xxx (xx.x%)	xxx (xx.x%)	xxx (xx.x%)
Halfway house	xxx (xx.x%)	xxx (xx.x%)	xxx (xx.x%)
Foster care	xxx (xx.x%)	xxx (xx.x%)	xxx (xx.x%)
Homeless or in no consistent shelter	xxx (xx.x%)	xxx (xx.x%)	xxx (xx.x%)
(Missing)	xxx (xx.x%)	xxx (xx.x%)	xxx (xx.x%)

Loss of Employment due to COVID-19	xxx (xx.x%)	xxx (xx.x%)	xxx (xx.x%)
(Missing)	xxx (xx.x%)	xxx (xx.x%)	xxx (xx.x%)
Current employment status			
Working now	N/A	xxx (xx.x%)	xxx (xx.x%)
Temporarily laid off/sick leave/maternity leave	N/A	xxx (xx.x%)	xxx (xx.x%)
Unemployed	N/A	xxx (xx.x%)	xxx (xx.x%)
Retired	N/A	xxx (xx.x%)	xxx (xx.x%)
Permanently/temporarily disabled	N/A	xxx (xx.x%)	xxx (xx.x%)
Keeping house	N/A	xxx (xx.x%)	xxx (xx.x%)
Student	xxx (xx.x%)	xxx (xx.x%)	xxx (xx.x%)
Other	xxx (xx.x%)	xxx (xx.x%)	xxx (xx.x%)
(Missing)	xxx (xx.x%)	xxx (xx.x%)	xxx (xx.x%)
Essential worker	N/A	xxx (xx.x%)	xxx (xx.x%)
(Missing)	N/A	xxx (xx.x%)	xxx (xx.x%)
Work place			
Nursing care facilities	N/A	xxx (xx.x%)	xxx (xx.x%)
Visiting nurse/home health aide service	N/A	xxx (xx.x%)	xxx (xx.x%)
Building cleaning services	N/A	xxx (xx.x%)	xxx (xx.x%)
Public transportation	N/A	xxx (xx.x%)	xxx (xx.x%)
Corrections facility	N/A	xxx (xx.x%)	xxx (xx.x%)
EMT or paramedic services	N/A	xxx (xx.x%)	xxx (xx.x%)
Meat packing farm facility	N/A	xxx (xx.x%)	xxx (xx.x%)
Agriculture and food production	N/A	xxx (xx.x%)	xxx (xx.x%)
Grocery store	N/A	xxx (xx.x%)	xxx (xx.x%)
Construction	N/A	xxx (xx.x%)	xxx (xx.x%)
(Missing)	N/A	xxx (xx.x%)	xxx (xx.x%)
Health Insurance			
No health insurance	xxx (xx.x%)	xxx (xx.x%)	xxx (xx.x%)
Private insurance	xxx (xx.x%)	xxx (xx.x%)	xxx (xx.x%)
Public insurance (Medicare/Medicaid/Tricare)	xxx (xx.x%)	xxx (xx.x%)	xxx (xx.x%)
(Missing)	xxx (xx.x%)	xxx (xx.x%)	xxx (xx.x%)

Loss Health Coverage due to COVID-19 Pandemic	xxx (xx.x%)	xxx (xx.x%)	xxx (xx.x%)
(Missing)	xxx (xx.x%)	xxx (xx.x%)	xxx (xx.x%)
Language Spoken Other than English	xxx (xx.x%)	xxx (xx.x%)	xxx (xx.x%)
(Missing)	xxx (xx.x%)	xxx (xx.x%)	xxx (xx.x%)
Family Income			
Less than \$15,000	xxx (xx.x%)	xxx (xx.x%)	xxx (xx.x%)
\$15,000 - \$19,999	xxx (xx.x%)	xxx (xx.x%)	xxx (xx.x%)
\$20,000 - \$24,999	xxx (xx.x%)	xxx (xx.x%)	xxx (xx.x%)
\$25,000 - \$34,999	xxx (xx.x%)	xxx (xx.x%)	xxx (xx.x%)
\$35,000 - \$49,999	xxx (xx.x%)	xxx (xx.x%)	xxx (xx.x%)
\$50,000 - \$74,999	xxx (xx.x%)	xxx (xx.x%)	xxx (xx.x%)
\$75,000 - \$99,999	xxx (xx.x%)	xxx (xx.x%)	xxx (xx.x%)
\$100,000 and above	xxx (xx.x%)	xxx (xx.x%)	xxx (xx.x%)
(Missing)	xxx (xx.x%)	xxx (xx.x%)	xxx (xx.x%)
Getting the Needed Health Care during COVID-19			
No, not a challenge	xxx (xx.x%)	xxx (xx.x%)	xxx (xx.x%)
Yes, a minor challenge	xxx (xx.x%)	xxx (xx.x%)	xxx (xx.x%)
Yes, this is a major challenge	xxx (xx.x%)	xxx (xx.x%)	xxx (xx.x%)
(Missing)	xxx (xx.x%)	xxx (xx.x%)	xxx (xx.x%)
Have A Place to Stay/Live during COVID-19			
No, not a challenge	xxx (xx.x%)	xxx (xx.x%)	xxx (xx.x%)
Yes, a minor challenge	xxx (xx.x%)	xxx (xx.x%)	xxx (xx.x%)
Yes, this is a major challenge	xxx (xx.x%)	xxx (xx.x%)	xxx (xx.x%)
(Missing)	xxx (xx.x%)	xxx (xx.x%)	xxx (xx.x%)
Getting Enough Food to Eat during COVID-19			
No, not a challenge	xxx (xx.x%)	xxx (xx.x%)	xxx (xx.x%)
Yes, a minor challenge	xxx (xx.x%)	xxx (xx.x%)	xxx (xx.x%)
Yes, this is a major challenge	xxx (xx.x%)	xxx (xx.x%)	xxx (xx.x%)
(Missing)	xxx (xx.x%)	xxx (xx.x%)	xxx (xx.x%)
Having Clean Water to Drink during COVID-19			
No, not a challenge	xxx (xx.x%)	xxx (xx.x%)	xxx (xx.x%)

Yes, a minor challenge	xxx (xx.x%)	xxx (xx.x%)	xxx (xx.x%)
Yes, this is a major challenge	xxx (xx.x%)	xxx (xx.x%)	xxx (xx.x%)
(Missing)	xxx (xx.x%)	xxx (xx.x%)	xxx (xx.x%)
Getting the Needed Medicine during COVID-19			
No, not a challenge	xxx (xx.x%)	xxx (xx.x%)	xxx (xx.x%)
Yes, a minor challenge	xxx (xx.x%)	xxx (xx.x%)	xxx (xx.x%)
Yes, this is a major challenge	xxx (xx.x%)	xxx (xx.x%)	xxx (xx.x%)
(Missing)	xxx (xx.x%)	xxx (xx.x%)	xxx (xx.x%)
Getting to Needed-to-Go Place during COVID-19			
No, not a challenge	xxx (xx.x%)	xxx (xx.x%)	xxx (xx.x%)
Yes, a minor challenge	xxx (xx.x%)	xxx (xx.x%)	xxx (xx.x%)
Yes, this is a major challenge	xxx (xx.x%)	xxx (xx.x%)	xxx (xx.x%)
(Missing)	xxx (xx.x%)	xxx (xx.x%)	xxx (xx.x%)
Health Conditions			
Immunocompromised condition	xxx (xx.x%)	xxx (xx.x%)	xxx (xx.x%)
Autoimmune disease	xxx (xx.x%)	xxx (xx.x%)	xxx (xx.x%)
Hypertension	xxx (xx.x%)	xxx (xx.x%)	xxx (xx.x%)
Diabetes	xxx (xx.x%)	xxx (xx.x%)	xxx (xx.x%)
Chronic kidney disease	xxx (xx.x%)	xxx (xx.x%)	xxx (xx.x%)
Cancer diagnosis and/or treatment within the past 12	xxx (xx.x%)	xxx (xx.x%)	xxx (xx.x%)
Cardiovascular disease	xxx (xx.x%)	xxx (xx.x%)	xxx (xx.x%)
Asthma	xxx (xx.x%)	xxx (xx.x%)	xxx (xx.x%)
Chronic obstructive pulmonary disease	xxx (xx.x%)	xxx (xx.x%)	xxx (xx.x%)
Other chronic lung disease	xxx (xx.x%)	xxx (xx.x%)	xxx (xx.x%)
Sickle cell anemia	xxx (xx.x%)	xxx (xx.x%)	xxx (xx.x%)
Depression	xxx (xx.x%)	xxx (xx.x%)	xxx (xx.x%)
Alcohol or substance use disorder	xxx (xx.x%)	xxx (xx.x%)	xxx (xx.x%)
Intravenous drug use	xxx (xx.x%)	xxx (xx.x%)	xxx (xx.x%)
Other mental health disorder	xxx (xx.x%)	xxx (xx.x%)	xxx (xx.x%)
Other chronic condition	xxx (xx.x%)	xxx (xx.x%)	xxx (xx.x%)
(Missing)	xxx (xx.x%)	xxx (xx.x%)	xxx (xx.x%)

Note:

- a. The total N is number of participants who consented to participate in the Baseline Survey.
- b. Participants could check all Race and Health Conditions that apply.
- c. The denominator for pregnancy is number of participants who are age 18 and beyond, biological female and also self-identify gender as woman.

Table 2. Participant COVID-19 Testing and Symptoms in Baseline Survey in Merced County, CA

COVID-19 Testing and Symptoms	Minor (N=xxx)	Adult (N=xxx)	All Respondents (N=xxx) ^a
Able to isolate without losing job if participant tests positive for COVID-19	xxx (xx.x%)	xxx (xx.x%)	xxx (xx.x%)
(Missing)	xxx (xx.x%)	xxx (xx.x%)	xxx (xx.x%)
Able to quarantine without losing job if participant tests positive for COVID-19	xxx (xx.x%)	xxx (xx.x%)	xxx (xx.x%)
(Missing)	xxx (xx.x%)	xxx (xx.x%)	xxx (xx.x%)
Participant has been tested for COVID-19	xxx (xx.x%)	xxx (xx.x%)	xxx (xx.x%)
(Missing)	xxx (xx.x%)	xxx (xx.x%)	xxx (xx.x%)
Participant has been tested positive for COVID-19	xxx (xx.x%)	xxx (xx.x%)	xxx (xx.x%)
(Missing)	xxx (xx.x%)	xxx (xx.x%)	xxx (xx.x%)
Month of first positive test for COVID-19			
January	xxx (xx.x%)	xxx (xx.x%)	xxx (xx.x%)
February	xxx (xx.x%)	xxx (xx.x%)	xxx (xx.x%)
March	xxx (xx.x%)	xxx (xx.x%)	xxx (xx.x%)
April	xxx (xx.x%)	xxx (xx.x%)	xxx (xx.x%)
May	xxx (xx.x%)	xxx (xx.x%)	xxx (xx.x%)
June	xxx (xx.x%)	xxx (xx.x%)	xxx (xx.x%)
July	xxx (xx.x%)	xxx (xx.x%)	xxx (xx.x%)
August	xxx (xx.x%)	xxx (xx.x%)	xxx (xx.x%)
September	xxx (xx.x%)	xxx (xx.x%)	xxx (xx.x%)
October	xxx (xx.x%)	xxx (xx.x%)	xxx (xx.x%)
November	xxx (xx.x%)	xxx (xx.x%)	xxx (xx.x%)
December	xxx (xx.x%)	xxx (xx.x%)	xxx (xx.x%)
(Missing)	xxx (xx.x%)	xxx (xx.x%)	xxx (xx.x%)

Year of first positive test for COVID-19			
2019	xxx (xx.x%)	xxx (xx.x%)	xxx (xx.x%)
2020	xxx (xx.x%)	xxx (xx.x%)	xxx (xx.x%)
2021	xxx (xx.x%)	xxx (xx.x%)	xxx (xx.x%)
2022	xxx (xx.x%)	xxx (xx.x%)	xxx (xx.x%)
(Missing)	xxx (xx.x%)	xxx (xx.x%)	xxx (xx.x%)
Month of most recent test for COVID-19			
January	xxx (xx.x%)	xxx (xx.x%)	xxx (xx.x%)
February	xxx (xx.x%)	xxx (xx.x%)	xxx (xx.x%)
March	xxx (xx.x%)	xxx (xx.x%)	xxx (xx.x%)
April	xxx (xx.x%)	xxx (xx.x%)	xxx (xx.x%)
May	xxx (xx.x%)	xxx (xx.x%)	xxx (xx.x%)
June	xxx (xx.x%)	xxx (xx.x%)	xxx (xx.x%)
July	xxx (xx.x%)	xxx (xx.x%)	xxx (xx.x%)
August	xxx (xx.x%)	xxx (xx.x%)	xxx (xx.x%)
September	xxx (xx.x%)	xxx (xx.x%)	xxx (xx.x%)
October	xxx (xx.x%)	xxx (xx.x%)	xxx (xx.x%)
November	xxx (xx.x%)	xxx (xx.x%)	xxx (xx.x%)
December	xxx (xx.x%)	xxx (xx.x%)	xxx (xx.x%)
(Missing)	xxx (xx.x%)	xxx (xx.x%)	xxx (xx.x%)
Year of most recent test for COVID-19			
2019	xxx (xx.x%)	xxx (xx.x%)	xxx (xx.x%)
2020	xxx (xx.x%)	xxx (xx.x%)	xxx (xx.x%)
2021	xxx (xx.x%)	xxx (xx.x%)	xxx (xx.x%)
2022	xxx (xx.x%)	xxx (xx.x%)	xxx (xx.x%)
(Missing)	xxx (xx.x%)	xxx (xx.x%)	xxx (xx.x%)
Result of most recent test for COVID-19			
Negative	xxx (xx.x%)	xxx (xx.x%)	xxx (xx.x%)
Positive	xxx (xx.x%)	xxx (xx.x%)	xxx (xx.x%)
Never obtained results	xxx (xx.x%)	xxx (xx.x%)	xxx (xx.x%)
Indeterminate	xxx (xx.x%)	xxx (xx.x%)	xxx (xx.x%)

(Missing)	xxx (xx.x%)	xxx (xx.x%)	xxx (xx.x%)
Method of most recent test for COVID-19			
Nasal swab	xxx (xx.x%)	xxx (xx.x%)	xxx (xx.x%)
Throat swab	xxx (xx.x%)	xxx (xx.x%)	xxx (xx.x%)
Blood sample	xxx (xx.x%)	xxx (xx.x%)	xxx (xx.x%)
Saliva	xxx (xx.x%)	xxx (xx.x%)	xxx (xx.x%)
(Missing)	xxx (xx.x%)	xxx (xx.x%)	xxx (xx.x%)
Participant knows where to get COVID-19 testing in			
Strongly disagree	xxx (xx.x%)	xxx (xx.x%)	xxx (xx.x%)
Disagree	xxx (xx.x%)	xxx (xx.x%)	xxx (xx.x%)
Neither disagree or agree	xxx (xx.x%)	xxx (xx.x%)	xxx (xx.x%)
Agree	xxx (xx.x%)	xxx (xx.x%)	xxx (xx.x%)
Strongly agree	xxx (xx.x%)	xxx (xx.x%)	xxx (xx.x%)
(Missing)	xxx (xx.x%)	xxx (xx.x%)	xxx (xx.x%)
Participant thinks it is easy to get tested for COVID-19			
Strongly disagree	xxx (xx.x%)	xxx (xx.x%)	xxx (xx.x%)
Disagree	xxx (xx.x%)	xxx (xx.x%)	xxx (xx.x%)
Neither disagree or agree	xxx (xx.x%)	xxx (xx.x%)	xxx (xx.x%)
Agree	xxx (xx.x%)	xxx (xx.x%)	xxx (xx.x%)
Strongly agree	xxx (xx.x%)	xxx (xx.x%)	xxx (xx.x%)
(Missing)	xxx (xx.x%)	xxx (xx.x%)	xxx (xx.x%)
Participant has the following symptoms during the past week			
Fever or chills	xxx (xx.x%)	xxx (xx.x%)	xxx (xx.x%)
Cough	xxx (xx.x%)	xxx (xx.x%)	xxx (xx.x%)
Shortness of breath or difficulty breathing	xxx (xx.x%)	xxx (xx.x%)	xxx (xx.x%)
Lack of energy or general tired feeling	xxx (xx.x%)	xxx (xx.x%)	xxx (xx.x%)
Muscle or body aches	xxx (xx.x%)	xxx (xx.x%)	xxx (xx.x%)
Headache	xxx (xx.x%)	xxx (xx.x%)	xxx (xx.x%)
New loss of taste or smell	xxx (xx.x%)	xxx (xx.x%)	xxx (xx.x%)
Sore throat, congestion or runny nose	xxx (xx.x%)	xxx (xx.x%)	xxx (xx.x%)

Feeling sick to your stomach or vomiting, diarrhea	xxx (xx.x%)	xxx (xx.x%)	xxx (xx.x%)
Abdominal pain	xxx (xx.x%)	xxx (xx.x%)	xxx (xx.x%)
Skin rash	xxx (xx.x%)	xxx (xx.x%)	xxx (xx.x%)
Other	xxx (xx.x%)	xxx (xx.x%)	xxx (xx.x%)
(Missing)	xxx (xx.x%)	xxx (xx.x%)	xxx (xx.x%)

Note:

- a. The total N is number of participants who consented to participate in the Baseline Survey.

Table 3. Participant Attitudes towards SARS CoV-2 vaccination in Baseline Survey in Merced County, CA

Vaccination Acceptance	Minor (N=xxx)	Adult (N=xxx)	All Respondents (N=xxx) ^a
Participant has received a flu vaccine	xxx (xx.x%)	xxx (xx.x%)	xxx (xx.x%)
(Missing)	xxx (xx.x%)	xxx (xx.x%)	xxx (xx.x%)
Participant has received a flu vaccine in the last 12 months	xxx (xx.x%)	xxx (xx.x%)	xxx (xx.x%)
(Missing)	xxx (xx.x%)	xxx (xx.x%)	xxx (xx.x%)
Participant has received a COVID-19 vaccine	xxx (xx.x%)	xxx (xx.x%)	xxx (xx.x%)
(Missing)	xxx (xx.x%)	xxx (xx.x%)	xxx (xx.x%)
Likelihood to get an approved COVID-19 vaccine when it becomes available			
Definitely not	xxx (xx.x%)	xxx (xx.x%)	xxx (xx.x%)
Not at all likely	xxx (xx.x%)	xxx (xx.x%)	xxx (xx.x%)
Not too likely	xxx (xx.x%)	xxx (xx.x%)	xxx (xx.x%)
Fairly likely	xxx (xx.x%)	xxx (xx.x%)	xxx (xx.x%)
Very likely	xxx (xx.x%)	xxx (xx.x%)	xxx (xx.x%)
(Missing)	xxx (xx.x%)	xxx (xx.x%)	xxx (xx.x%)
Reason of getting a COVID-19 vaccine^b			
I want to keep my family safe	xxx (xx.x%)	xxx (xx.x%)	xxx (xx.x%)
I want to keep my community safe	xxx (xx.x%)	xxx (xx.x%)	xxx (xx.x%)
I want to keep myself safe	xxx (xx.x%)	xxx (xx.x%)	xxx (xx.x%)
I have a chronic health problem, like asthma or diabetes	xxx (xx.x%)	xxx (xx.x%)	xxx (xx.x%)
My doctor told me to get a COVID-19 vaccine	xxx (xx.x%)	xxx (xx.x%)	xxx (xx.x%)
I don't want to get really sick from COVID-19	xxx (xx.x%)	xxx (xx.x%)	xxx (xx.x%)
I want to feel safe around other people	xxx (xx.x%)	xxx (xx.x%)	xxx (xx.x%)
I believe life won't go back to normal until most people get a COVID-19	xxx (xx.x%)	xxx (xx.x%)	xxx (xx.x%)
Required by my school or workplace	xxx (xx.x%)	xxx (xx.x%)	xxx (xx.x%)
Required for travel	xxx (xx.x%)	xxx (xx.x%)	xxx (xx.x%)
Other	xxx (xx.x%)	xxx (xx.x%)	xxx (xx.x%)
(Missing)	xxx (xx.x%)	xxx (xx.x%)	xxx (xx.x%)

Reason of NOT getting a COVID-19 vaccine ^c			
I'm allergic to vaccines	xxx (xx.x%)	xxx (xx.x%)	xxx (xx.x%)
I don't like needles	xxx (xx.x%)	xxx (xx.x%)	xxx (xx.x%)
I'm not concerned about getting really sick from COVID-19	xxx (xx.x%)	xxx (xx.x%)	xxx (xx.x%)
I'm concerned about side effects from the vaccines	xxx (xx.x%)	xxx (xx.x%)	xxx (xx.x%)
I don't think vaccines work very well	xxx (xx.x%)	xxx (xx.x%)	xxx (xx.x%)
I don't trust that the vaccines will be safe	xxx (xx.x%)	xxx (xx.x%)	xxx (xx.x%)
I don't believe the COVID-19 pandemic is as bad as some people say it is	xxx (xx.x%)	xxx (xx.x%)	xxx (xx.x%)
I don't want to pay for it	xxx (xx.x%)	xxx (xx.x%)	xxx (xx.x%)
I don't know enough about how well a COVID-19 vaccine works	xxx (xx.x%)	xxx (xx.x%)	xxx (xx.x%)
Other	xxx (xx.x%)	xxx (xx.x%)	xxx (xx.x%)
(Missing)	xxx (xx.x%)	xxx (xx.x%)	xxx (xx.x%)

Note:

- a. The total N is number of participants who consented to participate in the Baseline Survey.
- b. Participants could check all that apply on Reason of Getting a COVID-19 Vaccine.
- c. Participants could check all that apply on Reason of Not Getting a COVID-19 Vaccine.

Table 4. Participant Infection Risk in Work Place in Baseline Survey in Merced County, CA

Work Place Infection Risk	Adult (N=xxx)^a
Participant has access to necessary facilities to wash in work place	
Not at all	xxx (xx.x%)
Rarely	xxx (xx.x%)
Some of the time	xxx (xx.x%)
Yes, most of the time	xxx (xx.x%)
Yes, all of the time	xxx (xx.x%)
(Missing)	xxx (xx.x%)
Participant is in close contact (i.e. within 6 ft) with others in work place	
Not at all	xxx (xx.x%)
Rarely	xxx (xx.x%)
Some of the time	xxx (xx.x%)
Yes, most of the time	xxx (xx.x%)
Yes, all of the time	xxx (xx.x%)
(Missing)	xxx (xx.x%)
Participant has access to necessary personal protective equipment in work place	
Not at all	xxx (xx.x%)
Rarely	xxx (xx.x%)
Some of the time	xxx (xx.x%)
Yes, most of the time	xxx (xx.x%)
Yes, all of the time	xxx (xx.x%)
(Missing)	xxx (xx.x%)

Note:

a. The total N is number of participants who consented to participate in the Baseline Survey.

Table 5. Sociodemographic and Test-relevant Characteristics in Front Door Survey Entries in Merced County, CA

Characteristic	Total Entries (N=xxx) ^a
Age Category^b	
